7.1. Subject Inclusion Criteria

1. Successfully completed Study IPX203-B16-02.
2. Able to provide written informed consent prior to the conduct of any study-specific procedures.
3. Female subjects of childbearing potential must have a negative urine pregnancy test at the baseline visit (Visit 1).
4. Agrees to use a medically acceptable method of contraception throughout the study and for 6 weeks after completing the study. Medically acceptable methods of contraception that may be used by the subject and/or partner include but are not limited to: abstinence, oral contraception, NuvaRing or transdermal systems, diaphragm with vaginal spermicide, intrauterine device, condom and partner using vaginal spermicide, surgical sterilization (6 months), progestin implant or injection, or postmenopausal female (no menstrual period for >2 years) or vasectomy (>6 months).

7.2. Subject Exclusion Criteria

1. Intends to use any doses of Rytary or Duopa™ during this study.
2. Plans to use an investigational treatment other than IPX203 during the course of this study.
3. Neurosurgical ablation treatment for PD is planned or anticipated during the study period. Implantation of a deep brain stimulator (DBS) for the treatment of PD is permitted during this study.
4. Subjects who, in the opinion of the clinical investigator, should not participate in the study.

7.3. Subject Withdrawal Criteria

Site personnel should make every effort to conduct all protocol-specific procedures to complete the study. A subject may be discontinued from the study due to the following reasons:

1. Withdrawal by subject
2. Adverse event
3. Lack of efficacy
4. Study terminated by Sponsor
5. Protocol deviation
6. Noncompliance with study drug

7. Lost to follow-up
8. Death
9. Other

Subjects who withdraw early from the study will not be replaced. The reason or reasons for discontinuation will be specified and documented.

8. STUDY PROCEDURES

The procedures to be performed at each study visit are summarized in [Table 2](#).

Table 2: Events Schedule for Study IPX203-B16-03

	Visit 1 Baseline	9 Months of IPX203 Therapy					
		Study Drug Resupply Months 1-2	Visit 2	Study Drug Resupply Months 4-5	Visit 3	Study Drug Resupply Months 7-8	Visit 4/ Early Termination
Study Month	0		3		6		9
ICF and HIPAA Authorization	X						
Check Inclusion/Exclusion Criteria	X						
Update Medical History	X						
Physical Examination	X						X
Vital Signs	X		X		X		X
Weight	X		X		X		X
C-SSRS	X		X		X		X
Clinical Laboratory Tests	X		X		X		X
Urine Pregnancy Test	X						
ECG	X		X		X		X
MDS-UPDRS Parts I-IV	X		X		X		X
PGI-S	X		X		X		X
CGI-S	X		X		X		X
PDQ-39	X		X		X		X
GCSI	X						X
NMSS	X		X		X		X
PDSS-2	X		X		X		X
PAS	X		X		X		X
TSA			X		X		X

	Visit 1 Baseline	9 Months of IPX203 Therapy					
		Study Drug Resupply Months 1-2	Visit 2	Study Drug Resupply Months 4-5	Visit 3	Study Drug Resupply Months 7-8	Visit 4/ Early Termination
Study Month	0		3		6		9
ZBI-12	X		X		X		X
EMSQ	X		X		X		X
Contact phone calls			X		X		X
Contact IWRS to dispense study medication	X	X	X	X	X	X	
Collect empty medication bottles and any unused study drug/Perform study drug accountability		X	X	X	X	X	X
Adverse Events	X		X		X		X
Concomitant Medications	X		X		X		X

^a Visit 1 is expected to occur on the same day as the End-of-Study Visit (Visit 7) of Study IPX203-B16-02 but not later than 1 week. After the subject provides consent for this study, carry over and record information from procedures at the End-of-Study Visit of IPX203-B16-02 as the Baseline data for this study.

^b Subjects enrolled at sites in the United States (US) must sign HIPAA authorization prior to the conduct of any study-specific procedures.

^c Record vital signs (blood pressure, heart rate, respiratory rate, and temperature [Visit 1 and Study Exit only]) after subject has been resting supine for at least 5 minutes, then record orthostatic blood pressure and heart rate after subject has been standing for approximately 2 minutes.

^d See [Appendix B](#).

^e See [Appendix C](#).

^f This test will be performed at Visit 1 of this study.

^g See [Appendix D](#).

^h See [Appendix E](#).

ⁱ See [Appendix F](#).

^j See [Appendix G](#).

^k See [Appendix H](#).

^l See [Appendix I](#).

^m See [Appendix J](#).

ⁿ See [Appendix K](#).

^o See [Appendix L](#).

^p See [Appendix M](#).

^q See [Appendix N](#).

r Contact phone calls for Visits 2 through 4:

- Following Visit 1, contact subjects weekly for the first month and then approximately monthly thereafter between visits to review the subject's medication dosing regimen.
- Instruct subjects to call the study site before making any changes to their IPX203 dosing regimen.
- Update and record concomitant medications and IPX203 dose adjustments.
- Contact subjects 1 day prior to Visits 2 to 4 to remind them to bring back any unused medication and empty medication bottles.

CGI-S = Clinical Global Impression of Severity Scale; C-SSRS = Columbia-Suicide Severity Rating Scale; ECG = electrocardiogram; EMSQ = Early Morning Symptoms Questionnaire; GCSI = Gastroparesis Cardinal Symptom Index; HIPAA = Health Insurance Portability and Accountability Act; ICF = informed consent form; IWRS = interactive web response system; PAS = Parkinson Anxiety Scale; PD = Parkinson's disease; PDQ-39 = 39-Item Parkinson's Disease Questionnaire; PDSS-2 = Parkinson's Disease Sleep Scale-2; PGI-S = Patient Global Impression of Severity Scale; MDS-UPDRS = MDS version of Unified Parkinson's Disease Rating Scale; NMSS = Non-Motor Symptom assessment scale for PD; TSA = Treatment Satisfaction Assessment; ZBI-12 = 12-Item Zarit Burden Interview.

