8.1. Visit 1 (Baseline)

Visit 1 is expected to occur on the same day as the End-of-Study Visit (Visit 7) of Study IPX203-B16-02. After the subject provides consent for this study, carry over and record information from procedures at the End-of-Study Visit of IPX203-B16-02 as the baseline data for this study.

After the subject has signed the informed consent (and HIPAA authorization for subjects at US sites), complete the following procedures and assessments:

- Review and record study entry criteria ([Section 7](#)).
- Update the subject's medical history.
- Perform urine pregnancy test for females of childbearing potential.
- Complete the 12-Item Zarit Burden Interview (ZBI-12) ([Appendix M](#)).
- Administer the Early Morning Symptoms Questionnaire (EMSQ) ([Appendix N](#)).
- Contact the interactive web response system (IWRS) to dispense study drug.
- Instruct the subject on dosing.
- After Visit 1, contact subjects weekly for the first month and then approximately monthly thereafter to discuss the subject's dosing regimen. Record the subject's current IPX203 dose regimen.
- Instruct subjects to call the study site before making any changes to their IPX203 dosing regimen.
- Subjects may return for study drug resupply approximately every 1 to 2 months as needed.

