12. ASSESSMENT OF SAFETY

12.1. Safety Parameters

Safety will be assessed by the following parameters:

- Electrocardiograms (ECGs), clinical laboratory tests, physical examinations, the Columbia-Suicide Severity Rating Scale (C-SSRS), and vital signs, including supine and standing orthostatic blood pressure and heart rate.
- Adverse events and concomitant medications will be evaluated throughout the course of the study.
- The Gastroparesis Cardinal Symptom Index (GCSI) at Screening, and Visit 4 (Exit) only.

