12.2.2. Recording Adverse Events

Elicit information about AEs with nonselective questions such as: “Have you experienced any changes in your health status since your last visit?” Encourage subjects to report AEs at onset.

Record information for any AE that emerges from the time the subject signs the ICF until Study Exit.

Monitor each subject closely for the development of AEs and record all such events on the AE page of the CRF. Whenever possible, group signs and symptoms that constitutes a single diagnosis. For example, cough, rhinitis, and sneezing might be grouped as upper respiratory infection.

For each AE, record the onset date, severity, seriousness, relationship to study medication, date of resolution (or continuing), action taken, and outcome in the CRF. The Investigator is to make a causality assessment (relationship to study medication) for every AE.

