- Treatment-related TEAEs
- AEs leading to discontinuation of the study medication
- TEAEs in subjects with COVID-19
- TEAEs by severity
- TEAEs by relationship to study drug.

TEAEs will also be presented by SOC, PT, treatment group and one of the following subgroups of AEs:

- Total daily dose on the day of AE onset, categorized as < 400, 400 to < 1000, 1000 to < 1400, 1400 to < 1800, 1800 to <= 2400, and >2400 mg
- Daily dosing frequency on the day of AE onset (2, 3, 4, etc. times a day)
- Time to first onset, defined as the study day of the first onset of AE of the given SOC or PT for the subject, categorized as <= 7 days, >7 to 30 days, >30 to 90 days, >90 to 180 days, and >180 days.
- Time period. In this analysis each AE will be assigned to all (possibly several) time periods as in the previous paragraph during which the AE was active (i.e. after onset and prior to resolution).

TEAEs will also be presented by SOC, PT, treatment group and one of the following subgroups of subjects:

- Age: < 65, ≥ 65 years old at Visit 1
- Sex: Males, Females
- Race: Caucasians, non-Caucasians
- Region: North America or Europe
- PD duration at Visit 1: <8 years or ≥8 years
- Concomitant medications: the following non-exclusive subgroups will be defined for subjects taking concomitant medications of the following categories:

- Amantadine
- selective MAOB inhibitors
- anticholinergic PD medications
- dopamine agonists
- others

Additional summaries of non-treatment-emergent AEs that started in the previous study IPX203-B16-02 will be provided:

- AEs that started in study IPX203-B16-02 and resolved in the current study vs. those that did not resolve, by SOC, PT and treatment at the onset of AE (IPX203 or IR CD-LD and both treatments together)
- AEs that started in study IPX203-B16-02 and ended in the current study vs. are ongoing at the end of the current study by SOC, PT and treatment at the onset of AE (IPX203 or IR CD-LD and both treatments together)

For this analysis AE will be defined as resolved if its outcome is recorded as “Recovered/Resolved” or “Recovered/Resolved with Sequelae” in the eCRF. All other AEs will be considered not resolved.

The summaries by SOC and PT will be ordered alphabetically by SOC and PT.

Additionally number and percentage of subjects with TEAE will be presented by preferred term only in the descending order of total frequency.

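### The scheduled contact calls carry no adverse event question, so systematic AE questioning is first scheduled at Month 3, although the SAP tabulates onset within 7 and 30 days

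*Protocol*

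**What the plan says.** **Visits.** In protocol Table 2 the "Adverse Events" row is marked at Visits 1, 2, 3 and 4 (Months 0, 3, 6 and 9) and is blank in the drug-resupply columns. In the visit-by-visit text, the first instruction to record AEs after dosing starts is at Visit 2 (Section 8.2.2).

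**Calls.** Footnote r to Table 2 has sites "contact subjects weekly for the first month and then approximately monthly thereafter between visits" to review the dosing regimen, "Update and record concomitant medications and IPX203 dose adjustments", and remind subjects to return bottles. Section 8.1 has them "contact subjects weekly for the first month and then approximately monthly thereafter to discuss the subject's dosing regimen", and Sections 8.2.2 and 8.3.2 continue this at about monthly intervals. AEs are not named in any of these places.

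**AE collection in general.** Section 12.1 states that "Adverse events and concomitant medications will be evaluated throughout the course of the study". Section 12.2.2 offers a nonselective question by way of example, "Have you experienced any changes in your health status since your last visit". It also asks sites to encourage reporting at onset, to monitor closely, and to record every AE with its onset date.

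**Analysis.** SAP Section 5.1 presents treatment-emergent AEs by time to first onset, "categorized as <= 7 days, >7 to 30 days, >30 to 90 days, >90 to 180 days, and >180 days". It also presents them by total daily dose and by dosing frequency on the day of onset.

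**The concern.** Long-term safety is the first-named part of the study objective, and the calls already reach subjects often in the weeks after open-label IPX203 begins. Yet a site can follow the written call content exactly, log a dose reduction or a new concomitant drug by phone, and not be prompted to ask what event lay behind it.

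The early weeks matter most for subjects randomized to IR CD-LD in Study IPX203-B16-02, who return to IPX203 here, and the SAP splits its tables by that earlier arm. For context only, and not as a forecast: the protocol Introduction reports AEs in 10 of 28 subjects during IPX203 and 2 of 27 during IR CD-LD in an earlier study with 15-day treatment periods. The AEs seen there in two or more subjects were all mild or moderate.

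Two things are at stake: whether such events are captured at all, and whether their onset dates are good enough for the SAP tables. Dates have a specific consequence. SAP Section 2 calculates a relative day only from a complete date, and Section 5 does not impute missing safety data. Section 5.1, however, keeps an AE with a partial start date as treatment-emergent unless the known parts rule that out. An event recalled only to the month would therefore count in the overall incidence but have no study day for the onset table, and the SAP gives no rule for assigning its dose on the onset day.

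**Working it through.** The plan states no figure for this point, so there is none to reproduce. The check compares the passages and then counts days.

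**Step 1: is an AE question on the calls implied?** The Concomitant Medications row of Table 2 has the same pattern as the AE row: Visits 1 to 4 only. Footnote r then extends concomitant medications to the calls in words. It makes no such extension for AEs, and Sections 8.1 to 8.3 do not either. No other section schedules an AE question or AE recording at a call.

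**Step 2: inputs for the day count.**
- Visit 2 at Month 3: 3 × 30.44 = 91.3, taken as day 91.
- Onset categories from SAP 5.1: days 1–7, 8–30 and 31–90 precede Visit 2.
- Call days are an assumption built from footnote r: 7, 14, 21 and 28 (weekly), then about 58 (monthly), with the reminder call on day 90. A further monthly call before Visit 2 is possible, so there are 5 to 6 routine calls plus the reminder.
- Onset is taken as uniform over days within each category (assumption).

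**Step 3: formula.** Gap = day of the next scheduled AE question − day of onset.

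As written, the next question for any onset in days 1–90 is on day 91:
- days 1–7: 91 − 7 = 84 to 91 − 1 = 90, mean 87
- days 8–30: 91 − 30 = 61 to 91 − 8 = 83, mean 72
- days 31–90: 91 − 90 = 1 to 91 − 31 = 60, mean 30.5
- days 1–90 overall: mean 45.5, maximum 90

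With the question added to the existing calls:

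| Onset days | Gap range | Sum of gaps / days | Mean |
|---|---|---|---|
| 1–7 | 0–6 | 21 / 7 | 3.0 |
| 8–30 | 0–29 | 120 / 23 | 5.2 |
| 31–90 | 0–31 | 874 / 60 | 14.6 |
| 1–90 | 0–31 | 1015 / 90 | 11.3 |

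The 29-day maximum in the second row comes from onsets on days 29–30, just after the last weekly call; up to day 28 the gap is at most 6 days.

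**Step 4: sensitivity.** If the reminder call is not used for the question, the overall mean is 11.6 days and the maximum 32. If Visit 2 is placed on day 90, each gap under the current text falls by one day, so onsets in days 1–7 wait 83 to 89 days. Either way, three of the five onset categories close by the first scheduled question.

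**The case against.** The strongest reply is that AE capture is not confined to visits. Section 12.2.2 requires close monitoring and the recording of all AEs from consent to Study Exit, and asks sites to encourage reporting at onset. A site that learns of an event on a call must record it. Serious AEs must be reported within 24 hours of the site's knowledge (Section 12.3.2). Appendix A advises telephone contact, especially in the initial weeks, to judge dose adjustment, with avoidance of troublesome dyskinesia and other dopaminergic side effects as part of the goal. Such a call may well bring out the events most relevant to a switch. Subjects are also told to phone before changing their regimen. The question tied to the last visit is only an example, not a fixed recall window. Subjects from the IPX203 arm are continuing the drug, and everyone starts on a regimen already set in the earlier dose-conversion period.

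Most of this stands. A reader might infer that early safety rests on three-month recall, or that no AE is actively sought in the switch period. The documents support neither reading, because the routes above operate between visits. A blank cell in Table 2 also does not by itself show that an item is collected only at visits, as the concomitant medication row demonstrates.

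What remains is narrower. None of these provisions schedules a nonselective AE question at a call. Appendix A concerns dose adjustment and contains no instruction to elicit or record AEs. The 24-hour rule starts only once the site knows of a serious event.

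**Conclusion.** The point holds in a limited form. For non-serious AEs in the first three months, systematic questioning is first scheduled at about day 91. Before that, ascertainment depends on what subjects volunteer, on a monitoring duty with no stated interval, and on what arises in dose-adjustment calls. The SAP's early onset categories and its dose-at-onset tables ask more of the data than this schedule secures, so mild or transient early events may be missed or misdated.

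The size of that effect is unknown. The 84 to 90 days for onsets in days 1–7 is the interval to the next scheduled question, not a measured recall delay; it applies to an event that was neither volunteered nor raised on a call. It would be tempting to state that treatment-emergent AE incidence is biased downward, but the documents give no rate of forgotten or misdated events, so this is a risk and not a finding. The comparison of average gaps (about 46 against about 11 days) rests on the assumed call days and uniform onset.

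This is a low-cost improvement to AE ascertainment and onset dating in a descriptive safety extension. It does not invalidate the planned analyses.

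**What to change.** - In footnote r and in the call bullets of Sections 8.1, 8.2.2 and 8.3.2, add that at each contact call the site asks the nonselective AE question and records any AE with its onset date, together with the reason for any dose adjustment.
- Mark the contact calls in the AE row of Table 2, and carry the same change into the schedule reproduced in SAP Section 9.1.
- In Section 12.2.2, reword the example question so that it refers to the last visit or call.

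This needs no new calls, visits or staff. Calls will run slightly longer, and recorded AE rates may rise somewhat.

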8.1. Visit 1 (Baseline)

Visit 1 is expected to occur on the same day as the End-of-Study Visit (Visit 7) of Study IPX203-B16-02. After the subject provides consent for this study, carry over and record information from procedures at the End-of-Study Visit of IPX203-B16-02 as the baseline data for this study.

After the subject has signed the informed consent (and HIPAA authorization for subjects at US sites), complete the following procedures and assessments:

- Review and record study entry criteria ([Section 7](#)).
- Update the subject's medical history.
- Perform urine pregnancy test for females of childbearing potential.
- Complete the 12-Item Zarit Burden Interview (ZBI-12) ([Appendix M](#)).
- Administer the Early Morning Symptoms Questionnaire (EMSQ) ([Appendix N](#)).
- Contact the interactive web response system (IWRS) to dispense study drug.
- Instruct the subject on dosing.
- After Visit 1, contact subjects weekly for the first month and then approximately monthly thereafter to discuss the subject's dosing regimen. Record the subject's current IPX203 dose regimen.
- Instruct subjects to call the study site before making any changes to their IPX203 dosing regimen.
- Subjects may return for study drug resupply approximately every 1 to 2 months as needed.

8.2. Visit 2 (Month 3)

8.2.1. Prior to Visit 2

Call the subjects prior to Visit 2 and remind them to bring any unused study medication and empty medication bottles to Visit 2.

8.2.2. At Visit 2

- Collect unused study drug and empty bottles.
- Review study drug accountability.
- Update IPX203 regimen (dose, frequency, number of capsules) and concomitant medications.
- Assess vital signs after subject is supine for at least 5 minutes (blood pressure, heart rate, temperature and respiratory rate) and then assess orthostatic blood pressure and heart rate after subject is standing for approximately 2 minutes.
- Record AEs.

- Weigh the subject.
- Perform a 12-lead ECG.
- Administer C-SSRS ([Appendix B](#))
- Collect blood and urine samples for clinical laboratory studies ([Appendix C](#)).
- Administer MDS-UPDRS Parts I through IV ([Appendix D](#)).
- Determine PGI-S and CGI-S scores ([Appendix E](#) and [Appendix F](#), respectively).
- Complete PDQ-39 ([Appendix G](#)).
- Perform NMSS ([Appendix I](#)).
- Complete the PDSS-2 ([Appendix J](#)).
- Complete PAS ([Appendix K](#)).
- Complete TSA ([Appendix L](#)).
- Complete the ZBI-12 ([Appendix M](#)).
- Administer the EMSQ ([Appendix N](#)).
- Contact IWRS and enter study drug dispensing information.
- Dispense study drug and provide dosing instructions.
- Subjects may return for study drug resupply approximately every 1 to 2 months as needed.
- Instruct subjects to call the study site before making any changes to their IPX203 dosing regimen.
- Call subjects approximately monthly to discuss IPX203 dosing. Record the subject's current IPX203 dose regimen.

8.3. Visit 3 (Month 6)

8.3.1. Prior to Visit 3

Call the subjects prior to Visit 3 and remind them to bring any unused study medication and empty medication bottles to Visit 3.

8.3.2. At Visit 3

- Collect unused study drug and empty bottles.
- Review study drug accountability.
- Update IPX203 regimen (dose, frequency, number of capsules) and other concomitant medications.

- Assess vital signs after subject is supine for at least 5 minutes (blood pressure, heart rate, temperature and respiratory rate) and then assess orthostatic blood pressure and heart rate after subject is standing for approximately 2 minutes.
- Record AEs.
- Weigh the subject.
- Perform a 12-lead ECG.
- Administer C-SSRS ([Appendix B](#)).
- Collect blood and urine samples for clinical laboratory studies ([Appendix C](#)).
- Administer MDS-UPDRS Parts I through IV ([Appendix D](#)).
- Determine PGI-S and CGI-S scores ([Appendix E](#) and [Appendix F](#), respectively)
- Complete PDQ-39 ([Appendix G](#)).
- Perform NMSS ([Appendix I](#)).
- Complete the PDSS-2 ([Appendix J](#)).
- Complete PAS ([Appendix K](#)).
- Complete TSA ([Appendix L](#)).
- Complete the ZBI-12 ([Appendix M](#)).
- Administer the EMSQ ([Appendix N](#)).
- Contact IWRS and enter study drug dispensing information.
- Dispense study drug and provide dosing instructions.
- Subjects may return for study drug resupply approximately every 1 to 2 months as needed.
- Instruct subjects to call the study site before making any changes to their IPX203 dosing regimen.
- Call subjects approximately monthly to discuss IPX203 dosing. Record the subject's current IPX203 dose regimen.

8.4. Visit 4 – Study Completion (Month 9) or Early Discontinuation

8.4.1. Prior to Visit 4

Call the subjects prior to Visit 4 and remind them to bring any unused study medication and empty medication bottles to the visit.

8.4.2. At Visit 4

- Collect unused study drug and empty bottles.
- Review study drug accountability.

- Update IPX203 regimen (dose, frequency, number of capsules) and other concomitant medications.
- Assess vital signs after subject is supine for at least 5 minutes (blood pressure, heart rate, temperature and respiratory rate) and then assess orthostatic blood pressure and heart rate after subject is standing for approximately 2 minutes.
- Record AEs.
- Weigh the subject.
- Perform physical exam including weight.
- Perform a 12-lead ECG.
- Administer C-SSRS ([Appendix B](#)).
- Collect blood and urine samples for clinical laboratory studies ([Appendix C](#)).
- Administer MDS-UPDRS Parts I through IV ([Appendix D](#)).
- Determine PGI-S and CGI-S scores ([Appendix E](#) and [Appendix F](#), respectively).
- Complete PDQ-39 ([Appendix G](#)).
- Complete GCSI ([Appendix H](#)).
- Perform NMSS ([Appendix I](#)).
- Complete the PDSS-2 ([Appendix J](#)).
- Complete PAS ([Appendix K](#)).
- Complete the TSA ([Appendix L](#)).
- Complete the ZBI-12 ([Appendix M](#)).
- Administer the EMSQ ([Appendix N](#)).
- Contact IWRS to report subject disposition.

